2.7.5. Environmental risks

The gene treatment planned in this clinical trial does not involve particular risks in terms of public health. The cell infusion will occur in a dedicated room of the authorized area (Impianto Area for MOGM Class -MI/IC/IMP.2/01-002 Rev.2) in the Hematology and Bone Marrow Transplantation Unit, notified for the use of the specific GMOs.

The procedures and programs for the cleaning, disinfection and decontamination of the ward, the operating theater (if it is used) and the equipment do not differ from the standard ones in force for the management of patients who undergo bone marrow transplantation, according to Institutional SOPs.

All the solid and liquid waste contaminated by biological and/or potentially infected material are disposed of in compliance with the hospital regulations in force. All members of the staff, wearing gloves and a protection mask, are adequately educated and trained. In particular, the staff is shown how to apply the regulations in force to patients who receive multiple transfusions, are immunosuppressed and at high risk of infections.

In a recent review of the literature, no RCR was detected in 103 patients treated with *ex vivo* retrovirally transduced cells, nor in 342 patients treated *in vivo* with retroviral vectors ([Schenk-Braat et al. 2007](#)). Overall, in more than 18 years of clinical trials, there has been no report of cultural or molecular RCR test positivity, in more than 300 clinical trials conducted worldwide with retroviral vectors and a very high number of people considering healthcare staff, family members and other people. In addition, no RCL has been detected in the clinical trials currently conducted with SIN lentiviral vector ([Cartier N et al., Science 2009](#)). Even in the unlikely event of RCL, the risk of transmission is expected to be typical of a lipid membrane enveloped virus.

Therefore, risks for healthcare staff and others should be mostly limited to accidental venipuncture and accidental mucosal or parenteral exposure to body fluids. An emergency plan is active in the Hospital for this circumstance.

The patients will be followed to exclude the possible development of RCL infection (see above). Samples will be collected before treatment (at baseline) and after 1, 3, 6, 12 and 24 months, and then yearly after treatment, as suggested by FDA guidelines (Guidance for Industry, November 2006). In case the samples collected during the first two years result always negative for the screening tests HIV p24, VSV-G DNA and HIV-pol RNA, the subsequent yearly samples will be stored, but not analyzed. If one of the above- mentioned tests will result positive, the screening evaluations will be repeated at the next planned follow up visit; in the case two of the three screening test will result positive, a confirmatory RCL culture tests will be performed. Of note, HIV-derived RCL would conceivably be sensitive to – and treatable by – conventional anti-HIV therapy targeting all *pol*-derived enzymes (RT, protease and integrase). We can estimate that the risk of acquiring an infection by wild type HIV for the patients enrolled in the clinical study is superimposable to that of the population of the same age not under study.

2.8. Clinical trials performed in other countries with similar Drug Substance

2.8.1. Gene Therapy for Wiskott-Aldrich-Syndrome using a retroviral vector

Since 2006, a gene therapy clinical trial has been conducted in Hannover Medical School by Dr. [name]. The preliminary results have been presented at the 2008 American Society of Gene & Cell Therapy (ASGT) meeting and an update was given at the 2009 European Society for Blood and Marrow Transplantation (EBMT) Inborn Error meeting in Cambridge (UK). Ten patients were treated with infusion of autologous mobilized peripheral blood CD34+ cells transduced with a gammaretroviral vector encoding WASP, under the control of a viral promoter. All patients are alive, one patient underwent a bone marrow transplant due to failure of engraftment, associated with low dose of cells infused. The first two patients have reached >24 months of follow up and showed evidence of long-term gene marking in myeloid and lymphoid cells. Gene marking in myeloid cells is about 10-30%, in NK cells 50-80%, in T cells 80-95%. In addition, the majority of peripheral thrombocytes showed evidence of WASP expression and platelet counts have substantially improved. Functional reconstitution was documented in dendritic cells (podosome formation), T cells (proliferation in response to CD3-signaling), and NK cells (formation of immunological synapse). Of note, they did not develop any severe infections or bleeding after gene therapy. In the first patient eczema and autoimmune haemolytic anaemia have resolved, while anti-neutrophil and anti-PLT antibodies have disappeared. In the second patient eczema has resolved. Clinically, patients are in good conditions more than two years after gene therapy ([Boztug K et al, 2010](#)). These results are very encouraging and confirm our hypothesis that the mixed chimerism associated with reduced conditioning, also thanks to the occurrence of selective advantage, is sufficient to allow biological efficacy and clinical benefit. However, the majority of WAS patients treated with the retroviral vector encoding WASP have developed leukaemia during the study conducted in Germany ([name], [name] personal communication). As of January 2014, 7 out of the 10 treated patients developed acute leukaemia (one acute myeloid leukemia (AML), four T cell acute lymphoblastic leukemia (T-ALL), and two primary T-ALL with secondary AML, with all six cases of T-ALL associated with a

dominant clone with vector integration at the LMO2) ([Braun et al, 2014](#)). It should be noted that the lentiviral vector used in the present study has a different origin and it does not contain the part of the retroviral vector that is potentially responsible of the leukaemia. While more extensive studies and longer follow up will be needed to determine the overall safety profile of gene therapy with gamma-retroviral vector, this finding further reinforces the choice of a potentially safer platform, based on HIV vector for gene transfer in WAS.

2.8.2. Gene Therapy for Adrenoleukodystrophy using a lentiviral vector

As mentioned above, a clinical trial of gene therapy based on HSC and LV for the treatment of cerebral Adrenoleukodystrophy (ALD) was started at the Hôpital Saint-Vincent de Paul and Hôpital Necker in Paris ([Cartier N et al, Science 2009](#)). X-linked adrenoleukodystrophy (X-ALD), a genetic disorder secondary to alterations in the ABCD1 (ATP-binding cassette, sub-family D [ALD], member 1) gene, results in defective peroxisomal oxidation and the accumulation of very long chain fatty acids (VLCFA) in all tissues. The disorder primarily affects the adrenal cortex and the nervous system.

Up to now, three patients suffering from cerebral ALD have been included. Autologous CD34⁺ progenitor cells were collected from MPB and transduced *ex vivo* for 18 hours with a 3rd generation LV encoding the ALD protein cDNA under the control of the MND promoter. The LV used in this trial differs from the Drug Substance described in the present protocol for some aspects, including the presence in the transfer construct of a different promoter driving therapeutic gene expression, and the protocol of large scale GMP production. The gene transfer procedure of CD34⁺ cells was based on a similar cytokine combination to the one used for the preparation of the Medicinal Product described in the present protocol. Transduced cells were frozen after transduction to perform all tests planned before infusion. After thawing and prior to re-injection, 20-40% of the transduced CD34⁺ cells expressed the ALD protein with a mean of 0.7 copies of integrated provirus per cell. Transduced cells were re-infused into pharmacologically conditioned patients (receiving a full myeloablative regimen consisting of Busulfan and Cyclophosphamide). The first results of this study have shown that genetically modified CD34⁺ progenitor cells transduced with the ALD protein-encoding LV are able to differentiate in all hematopoietic lineages (granulocytes, monocytes, B and T lymphocytes) *in vivo*. The percentage of corrected lymphocytes and monocytes in the peripheral blood of treated patients remained stable from day 30 to the longest follow up (30 and 24 months for Pt 1 and Pt2, respectively). From 10% to 15% of CD14⁺, CD3⁺, CD19⁺ and CD3-CD56⁺ cells expressed the ALD protein. Test for vector-derived RCL and vector mobilization were negative up to the last follow up. Clinical and instrumental evaluations revealed stability of the disease and a course comparable to that of patients undergoing allogeneic HSC transplantation.

These results indicate that HSC gene therapy using HIV-1-derived LV is not associated with the emergence of RCL and vector mobilization, and that LV allow safe and efficient transduction of human HSC and maintenance of gene expression *in vivo*.

3. OBJECTIVES

The objective of the present gene therapy clinical trial is to evaluate the safety of the transduced stem cells infusion in patients affected by WAS after a reduced-intensity conditioning regimen and its efficacy in improving the patient's immune-function and thrombocytopenia.

3.1. Primary Objectives

1) To evaluate the safety of the administration of autologous CD34+ cells transduced with a lentiviral vector containing the WASP gene in patients with WAS, after a reduced intensity conditioning regimen.

The short-term and long-term safety of LV gene transfer into HSC will be evaluated on the basis of adverse event reporting and monitoring for the theoretical risk of systemic reactions to cell infusion, abnormal clonal proliferation and immune response to the transgene. Hematological reconstitution after non-fully myeloablative conditioning regimen will be closely monitored.

2) To evaluate the long-term engraftment of WASP-expressing transduced cells.

The proportion of multilineage WASP-expressing cells, indicating engraftment of repopulating transduced stem cells, will be evaluated at different time points after transplant.

3) To evaluate the efficacy of gene therapy assessed as:

3.1) Improvement of the patient's immune function, specifically of T cell function and antigen-specific responses to vaccinations

Improvement of *in vitro* T-cell functions and *in vivo* antibody production will be analyzed as part of the post-gene therapy follow up.

3.2) Improvement of thrombocytopenia

Increase in platelet count compared to baseline and normalization of mean platelet volume (MPV) at 1-year post treatment will be assessed according to the severity of thrombocytopenia before gene therapy.

3.2. Secondary objectives

A) To evaluate the efficacy of gene therapy in improving the patient's clinical conditions, assessed by reduction in frequency of severe infections, and bleeding episodes and reduction of autoimmunity phenomena and eczema.

A complete clinical and laboratory assessment of the patient after the proposed treatment is scheduled at different time points, to provide an overall evaluation of the clinical benefit.

4. INVESTIGATIONAL PLAN

This clinical study is based on *ex vivo* gene therapy for Wiskott-Aldrich syndrome using autologous hematopoietic stem/progenitor cells (purified CD34+ cells). Genetically modified cells will be re-infused to patients following a reduced intensity conditioning regimen (see chapter 10 for details), dispensed to eliminate the defective cells and favor the engraftment of gene corrected cells expressing a normal WASP. The eligibility of the patients will be evaluated according to enrolment criteria, which include patients suffering from a severe clinical condition or severe WAS phenotype, without a suitable matched donor for allogeneic transplant or ineligible for HSCT because of age > 5 years or for clinical features.

In this study, we plan to treat a total of 8 patients in a period of 5 years, which will be followed for the safety and efficacy endpoint measures. There is a *Follow Up phase* composed of an *Initial Follow Up period* of at least 3 years, when subjects are intended to reach the primary efficacy timepoint, and then a further *Long-Term Follow Up period* from 3 years up to 8 years. For patients who complete the *Follow Up phase*, from year 8 onwards there will be an additional extended long-term follow up (ELTFU) phase. During the ELTFU phase, patients will be contacted annually, in order to collect long-term safety and selected efficacy data, until a separate observational long-term follow-up (OLTFU) study is initiated, and patients have enrolled in it. Once the OLTFU study is set up, patients will be invited to enter the OLTFU study at any time after they have completed a minimum of 5 years follow up in this study (WAS Pivotal 201228).

The treatment will be administered at the Pediatric Immunohematology and Bone Marrow Transplantation Unit at the San Raffaele Scientific Institute in Milan, Italy. The investigators and the manufacturer of the product have a specialized expertise in hematopoietic stem cells manipulation, LV production and gene transfer procedure according to GMP standards. Clinical trials using the same lentiviral vectors have been implemented at the Institute for Child Health in London, Necker Hospital in Paris and Children's Hospital in Boston (see above). These clinical trials have adopted similar criteria for the enrolment of patients and similar safety and efficacy endpoints, but the conditioning regimen is different. The Genethon sponsored trial have adopted a myeloablative conditioning regimen based on the use of Busulfan 12 mg/kg, associated to Fludarabine (120 mg/sqm), possibly associated to anti-CD20 mAb and/or anti-Thymocyte globulin in the setting of autoimmunity. Information deriving from the preliminary results of the two trials will be exchanged and discussed in order to allow to define an optimal safe and efficacious conditioning for gene therapy in WAS patients.

4.1. Study Design

4.1.1. Type of study

This is a phase I/II, open label, non-randomized, prospective, single centre study.

4.1.2. Study duration

Enrolment phase: 5 years.

Starting date: April 2010

Follow Up phase: the *Follow Up phase* is composed of an *Initial Follow Up period* of at least 3 years after the reinfusion of transduced cells, when subjects are intended to reach the primary efficacy analysis endpoint, and then a further *Long-Term Follow Up period* from 3 up to 8 years after the reinfusion of transduced cells. In the *Initial Follow Up period*, patients will undergo regular follow up assessments to assess the efficacy and safety of the treatment.

Extended Long-Term Follow Up phase (ELTFU): patients who complete the *Follow Up phase* will then be contacted annually from year 8 onwards in order to collect long-term safety and selected efficacy data until a separate OLTFU study is initiated and patients have enrolled in it.

Once the OLTFU study is set up, patients will be invited to enter the OLTFU study at any time after they have completed a minimum of 5 years follow up in this study (WAS Pivotal 201228).

4.1.3. Study population

Patients of pediatric or adult age affected by WAS, with severe clinical phenotype and/or severe genetic mutation, who meet the inclusion/exclusion criteria described below.

4.2. Safety Endpoints

4.2.1. Primary safety endpoints

4.2.1.1. Safety of reduced conditioning regimen

a) *Hematological reconstitution.*

The absence of engraftment failure and prolonged aplasia (defined as ANC <500/ μ l at day +60, with no evidence of bone marrow recovery and requiring back-up administration) is assumed as proving the safety of reduced intensity conditioning regimen associated with the infusion of *ex vivo* transduced CD34 $^{+}$ cells.

In case the first two patients present prolonged aplasia, modification of the conditioning regimen is introduced in the third patient and the rule is again applied for this patient and the following two.

b) *Regimen related non-hematopoietic toxicity.*

A surveillance of clinical and laboratory parameters (for clinical features CTCAE ≥ 2 , for metabolic/laboratory CTCAE ≥ 3) of the treated patients (CTCAE will be applied during the first 100 days after transplant in order to assess the degree of morbidity associated to the reduced conditioning regimen).

Stopping rule: in case of 2 deaths occurring within 180 days from transplant (not superior to mortality reported from mismatched related donors, see [Table 1](#), [Table 2](#), [Table 3](#) and [Table 4](#)).

For detailed follow up and timing of clinical and laboratory surveillance see [Table 8a](#), [Table 8b](#) and [Table 10](#).

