	
I.v. ATG Thymoglobuline may be used at PI discretion in patients with clinical autoimmunity before day-18.

Inclusion criteria - Inclusion - Exclusion	
Inclusion Criteria
 
1) Diagnosis of WAS defined by genetic mutation and at least one of the following criteria:
 
 - Severe WAS mutation; - Absent WASP expression; - Severe clinical score (Zhu clinical score ≥ 3). 
2) No HLA-identical sibling donor
 
AND
 
3.1) Negative search for a matched unrelated donor (10/10) or an adequate unrelated cord blood donor (6/6) within 4-6 months;
 
OR
 
3.2) Patients of > 5 years of age who are not candidate to unrelated allogeneic transplant based on clinical conditions.
 
AND
 
4) Parental/guardian/patient signed informed consent.
 
Exclusion Criteria
 
Patients who meet any of the following criteria will be excluded from study admission:
 
 1) Patients positive for HIV-infection; 2) Patients affected by neoplasia; 3) Patients with cytogenetic alterations typical of MDS/AML; 4) Patients with end-organ functions or any other severe disease which, in the judgment of the investigator, would make the patient inappropriate for entry into this study; 5) Patients who underwent an allogeneic hematopoietic stem cell transplantation in the previous 6 months; 6) Patients who underwent an allogeneic hematopoietic stem cell transplantation with evidence of residual cells of donor origin.
Sample size	Eight patients will be treated in this study
Accrual/duration timeline	
Patients will undergo regular follow up after gene therapy to assess the efficacy and safety of the treatment.
 
1) For each subject the main study phase will be completed once the Initial Follow Up period of 3 years following treatment with OTL-103 is finished.
 
2) A Long- Term Follow up period will then be conducted from 3 years up to 8 years after the reinfusion of transduced cells.

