5.1.3. Sample size

Given the low frequency of disease and the degree of novelty of the proposed experimental approach, we plan to treat overall **8** patients, in an estimated 5-year period.

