8.3.2. Safety of the transduced cell infusion

Short-term safety of LV-transduced cell infusion consists in the absence of severe adverse reactions after infusion.

Microbiological contamination of the drug product: although all manipulations will be performed under validated GMP procedures, collection of bone marrow cells and their manipulation *ex vivo* is potentially associated with contamination. Standard operating procedures aimed at reducing this risk will be implemented during collection. The final results of the sterility test will be available after patient infusion. If a contamination is detected, the patient will receive a specific antibiotic treatment and a strict monitoring.

Long-term safety of LV-transduced cell infusion consists in the absence of RCL, abnormal clonal proliferation and immune responses against the transgene.

The overall safety of the experimental treatment will be evaluated on the basis of clinical and laboratory parameters recorded and monitored during the follow up of the treated patients, based on the assessment plan. A descriptive analysis will be performed on AE, AR, SAE/SAR, UAR, SUSAR, and events will be classified for frequency, severity and body system involved.

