12.3. Safety Endpoints

A descriptive analysis will be performed for all primary and secondary safety endpoints.

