10.1.1 Safety of Reduced Conditioning Regimen

Prolonged aplasia will be assessed based on Absolute Neutrophil Count (ANC) data collected at the Day 60 visit together with bone marrow recovery and back-up administration data (recorded in Adverse Event or Concomitant Medications page if there are any) for each subject. A listing of ANC data collected at Day 60 visit by subject will be generated. This will include all ANC data assessed in the visit window for Day 60 (from Day 47 to Day 76, Section [7.3.1](#)). The longitudinal profile of ANC for the whole post treatment phase as well as from baseline to 100 days post treatment will be described by means of two plots of individual patient data.

Regimen related non-hematopoietic toxicity will be assessed based on the clinical and laboratory data collected during the first 100 days post gene therapy (this is based on assessment of AEs with National Cancer Institute (NCI) CTCAE grade ≥ 2 for clinical features and NCI CTCAE grade ≥ 3 for laboratory parameters) for each subject. A summary and listing of clinical features NCI CTCAE grade ≥ 2 and laboratory features NCI CTCAE grade ≥ 3 during the first 100 days after gene therapy will be generated. Events are included based on the onset days from infusion.

To increase the informative clinical value of conditioning-related AEs, the 100 days period will be further stratified in three phases:

- Day 0-30
- Day 31 to Day 60
- Day 61 to Day 100

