10.1.2 Safety of Lentiviral (LVV) Gene Transfer into HSC

Short-term safety and tolerability will be evaluated based on adverse event reporting and monitoring of the systemic reactions to cell infusion (fever, tachycardia, nausea and vomiting, joint pain, skin rash). The short-term safety and tolerability of lentiviral-transduced cells infusion will be assessed by the absence of SAEs within 48 hours from infusion. A table of SAEs and AEs starting within 2 days of infusion will be generated by subject.

Long-term safety of LVV gene transfer consists of the absence of replication competent lentivirus (RCL) and abnormal clonal proliferation (ACP).

RCL is considered positive if a confirmatory RCL culture test is positive. In protocol amendment 11 (28 May 2020) the strategy for RCL testing was simplified: an HIV p24 antigen detection in the serum by ELISA is performed in the first instance. Should this test be positive, further analyses will be performed, including DNA PCR for VSV-G envelope on cells, and RT- PCR for HIV-pol RNA on serum. If a positive result is obtained from at least one of the additional tests, an appropriate confirmatory test may be performed. Prior to this, a confirmatory test was performed when two of the three screening tests (ELISA for HIV p24 antigen, DNA PCR for VSV-G env, and RT-PCR for HIV-pol RNA) were confirmed as having a positive result. The confirmatory test data will be summarised by visit. A listing of individual test data will be generated by subject together with anti-Human Immunodeficiency Virus (HIV) p24 antibodies and confirmatory RCL Culture test.

Monitoring for ACP requires the clinical review of multiple datasets (e.g., routine clinical and laboratory surveillance, repertoire study, bone marrow examination, integration site analysis). Therefore, no summary tables focused solely on ACP will be produced. Data needed for monitoring of ACP will be displayed in relevant AE and efficacy summaries. The results of the manual clinical review for ACP will be described in the CSR with cross-reference to the relevant study listings and a separate integration site analysis report.

A listing of adverse events with onset within 48 hours of gene therapy will be created.

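### Zero engraftment failures or aplasias is taken to prove the conditioning regimen safe, but 0 of 8 excludes only rates above about 32%, and no primary safety endpoint is given a confidence interval

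*Protocol*

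**What the plan says.** **Criterion.** Protocol 4.2.1.1(a), a primary safety endpoint, covers engraftment failure and prolonged aplasia (neutrophils below 500/µl at day +60, no marrow recovery, back-up cells needed). Their absence "is assumed as proving the safety of reduced intensity conditioning regimen". Protocol 8.3.1 restates this as a definition.

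Protocol 4.2.1.2 treats short-term safety as no serious adverse reaction within 48 hours, and long-term safety as no replication competent lentivirus (RCL) and no abnormal clonal proliferation (ACP). Protocol 8.3.2 reads: "Long-term safety of LV-transduced cell infusion consists in the absence of RCL, abnormal clonal proliferation and immune responses against the transgene". SAP 10.1.2 repeats the RCL and ACP part. The remaining primary item, non-haematological toxicity, is graded surveillance and not a zero-event criterion.

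**Size.** The synopsis states: "Eight patients will be treated in this study". Protocol 5.1.3 gives the reason: "Given the low frequency of disease and the degree of novelty of the proposed experimental approach". No tolerable event rate or precision target is given.

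**Analysis.** Protocol 12.3: "A descriptive analysis will be performed for all primary and secondary safety endpoints". Protocol 12.5 names Wilson intervals for proportions, and 12.4 calls for 95% intervals on the efficacy proportions. For aplasia, SAP 10.1.1 says: "A listing of ANC data collected at Day 60 visit by subject will be generated", and adds individual neutrophil plots. SAP 10.1.2 summarises RCL confirmatory results by visit and leaves ACP to clinical review without a summary table. SAP Table 10 ticks a summary table for prolonged aplasia, but the safety tables in Appendix 1 (16.3.1) contain none. In SAP section 10, only the anti-WASP antibody percentage (10.2.1), a secondary safety endpoint, is given a 95% interval.

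**The concern.** Safety is the first primary objective. The sentence in 4.2.1.1 is a rule of inference: no event seen, therefore safety shown. Eight patients cannot carry that inference, because a harm affecting a sizeable minority of patients can easily be absent from a sample of eight.

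The treatment of uncertainty is also uneven. Primary efficacy proportions and one secondary safety item receive intervals; the primary safety endpoints do not. A study report that followed the plan to the letter could state that conditioning safety was proven on 0/8, with nothing beside the zero to show how little it excludes.

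**Working it through.** **Inputs.** n = 8 treated patients (synopsis; Protocol 5.1.3). Zero-event criterion (Protocol 4.2.1.1, 4.2.1.2, 8.3.1, 8.3.2; SAP 10.1.2). Wilson method (Protocol 12.5). The documents give no tolerable rate and no calculation behind n, so there is no planned figure to reproduce. The true rates below are assumptions.

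**Step 1: what 0/8 excludes.**
- Wilson 95% upper limit for zero events: z²/(n + z²) = 3.84/(8 + 3.84) = 32.4%.
- Exact two-sided 95%: 1 − 0.025^(1/8) = 36.9%.
- Exact one-sided 95%: 1 − 0.05^(1/8) = 31.2%.

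On any of these, a true rate near 30% remains compatible with the data.

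**Step 2: how often the criterion would be met.** For one harm with true rate p per patient, all eight evaluable and every event detected, P(0/8) = (1 − p)^8.

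| Assumed true rate | P(0 of 8) |
|---|---|
| 5% | 66.3% |
| 10% | 43.0% |
| 15% | 27.2% |
| 20% | 16.8% |
| 30% | 5.8% |

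With seven evaluable patients and p = 10%, the chance is 0.9^7 = 47.8%.

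**Step 3: more than one harm.** The 43% holds for one harm at 10%, or for all harms combined at 10% per patient. Two independent harms at 10% each would both be absent with probability 0.9^16 = 18.5%.

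**Step 4: do the modification rules bound the rate?** Protocol 12.1 calls for modification if 2 of the first 3 patients have prolonged aplasia. At p = 10% that has probability 3 × 0.1² × 0.9 + 0.1³ = 2.8%. The rule is aimed at high rates and says little about moderate ones.

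**The case against.** Several points on the other side stand and limit what may be claimed.

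- **Proof is claimed once only.** It is attached to haematological reconstitution. A reader might infer that zero RCL or clonal events is also taken as proof. The text there defines the endpoint as absence of events, which is a statement of what is measured.
- **There is no formal safe/unsafe decision.** A reader might infer that a regimen with a 10% harm rate would be declared safe 43% of the time. The safety analysis is descriptive, and SAP section 7 says the study is not powered and all intervals are nominal. The 43% is the chance of meeting the protocol's own criterion, not the error rate of a planned test.
- **The 10% has no firm source.** It is tempting to take it from the retroviral trial in Protocol 2.8.1, where "one patient underwent a bone marrow transplant due to failure of engraftment" among ten treated. That trial used a different vector, the protocol links the failure to a low cell dose, and it does not show that the same definition of failure applied. The trial also had acute leukaemia in 7 of 10, so borrowing only its engraftment count would be selective. The 10% is therefore illustrative.
- **Count thresholds exist.** Protocol 12.1 lists modification and stopping rules and staggers the third patient. However, it calls the rules guidelines for discussion, and they set no limit on the rate. Separately, 4.2.1.1 triggers modification if the first two patients have aplasia while 12.1 says 2 of the first 3; these need reconciling.
- **Part of the reporting is already planned.** Appendix 1 has tables for positive RCL (14.3.1.3.1) and serious adverse events within 48 hours (14.3.1.2.1), and a neutrophil listing (16.2.8.5). A reader could compute an interval from x/n. Long follow-up and an envisaged pooled analysis (Protocol 12.6) also recognise that eight patients are not enough.

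These narrow the point to one unsupported sentence, missing intervals and a missing table. They do not remove it: a descriptive, unpowered analysis is a reason not to speak of proof.

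**Conclusion.** The point holds in this limited form. The inference in Protocol 4.2.1.1 is not supported by eight patients: 0/8 leaves rates up to 32.4% (Wilson) or 36.9% (exact two-sided) compatible with the data. No interval is planned for any primary safety endpoint, and the aplasia table ticked in SAP Table 10 is absent from Appendix 1.

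The limits rest on eight evaluable infused patients with complete detection; fewer would widen them. The 66%, 43% and 17% figures rest in addition on the assumed rates of 5%, 10% and 20% for a single harm.

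A reader might also infer that the trial is too small and should be enlarged. That does not follow: the sample size is explained by rarity and novelty, and the defect lies in the conclusion attached to it. The change is worth making because it alters what the report may conclude on a primary objective.

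**What to change.** 1. **Protocol 4.2.1.1:** replace the claim of proof with a statement that the observed proportion with engraftment failure or prolonged aplasia will be reported with its 95% interval.
2. **SAP 10.1.1 and 10.1.2:** report engraftment failure/prolonged aplasia, confirmed RCL, ACP (after the clinical review) and serious reactions within 48 hours as x/n of infused patients, each with the Wilson 95% interval of Protocol 12.5. Specify infused patients, because safety outputs default to the Mobilisation Set, which can include patients never infused; SAP Table 4 already allows safety analyses in the ITT set.
3. **SAP Appendix 1:** add the aplasia summary table that Table 10 ticks, and add the interval to tables 14.3.1.2.1 and 14.3.1.3.1. The 48-hour table counts serious adverse events whereas Protocol 4.2.1.2 refers to serious adverse reactions, so state which is counted.
4. **Interpretation:** state in the SAP and study report that 0/8 excludes only rates above about 32%, and draw no conclusion of proven safety from zero events.

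The cost is some rewording, one small table and a few added columns, using the Wilson option in SAS that SAP section 9 already names. The stated conclusion becomes less favourable. No new data, visits or patients are needed.
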